State of document: ***Released***

Document Number: ***Doc-00064398***

Revision: ***1***

Title: ***Assessing listening effort at different signal-to-noise ratios in bone-anchored users***

Owner: ***[name],[name]***

Reviewed by (Name, Initials, Date, Time):

[[name] ([name]) 11-Feb-2020 12:43:10 CET]

Approved by (Name, Initials, Date, Time):

[[name] ([name]) 11-Feb-2020 18:34:25 CET]

Released by (Name, Initials, Date, Time):

[[name] ([name]) 12-Feb-2020 15:10:17 CET]

Implemented (Date, Time):

Obsoleted by (Name, Initials, Date, Time):

File names:

BC103_Amendment1_signed.pdf ver.1,Doc-00064398.docx ver.4

	Title Assessing listening effort at different signal-to-noise ratios in bone-anchored users	Document no Doc-00064398	Revision 1
	Clinical Investigation Plan	State Released	Page 1(33)

Revision history

Revision no	Date	Description
0	16/07/19	Version 1 : version submitted to Ethics Committee
1	09/09/19	Version 2: comments from REC are addressed

Summary

Study site:	Queen Elizabeth, University Hospitals Birmingham NHS Foundation Trust; [name]
Investigation code:	BC103
Principal investigators:	[name], Consultant Clinical Scientist / Head of Audiology Services Audiology Department, [name], University Hospitals Birmingham [name]
Coordinating investigator	N/A
Sponsor:	Oticon Medical AB [name]
Monitor:	Oticon Medical representatives
Objective(s):	The primary objective of this study is to evaluate the decrease in pupil dilation when listening to speech-in-noise with OSN ON compared to OSN OFF at +4 dB SNR. Secondary and tertiary objectives are listed in Sec. 6.
Methodology:	Single-center, single-blinded, prospective study including three laboratory visits and a field trial period. Each participant will serve as his/her own control.
No of Patients:	30 patients are required for study completion.
Product:	Ponto 4 developed by Oticon Medical AB (Askim, Sweden) will be used for laboratory and field-trial testing. All devices and software used in this study are CE marked.

Main inclusion/exclusion criteria:	
Inclusion criteria
 
• Minimum 18 years and maximum 70 years old.• UK English mother tongue.• Bilateral conductive or mixed hearing loss.• Users fitted unilaterally or bilaterally on abutment.• Users are currently fitted with either Ponto 3, Ponto Plus or Ponto Pro (devices with a fitting range up to 45 dB HL).• Users with at least 6 months of daily experience with one Ponto sound processor.• BC thresholds of the implanted ear(s) better (lower) than or equal to 40 dB HL (average of 0.5, 1, 2 and 3 kHz) based on BC in-situ measurement at the first visit.• People currently employed/self-employed (since the Need for Recovery questionnaire refers to work-related fatigue).• Speech recognition scores better (higher) than or equal to 50% at +4 dB SNR with OSN OFF (as assessed via the first training list at Visit 1). This is to avoid including patients that are already “giving up” at +4 dB SNR.• Users entitled for a sound-processor upgrade (according to the investigator) will first be selected. If there are not enough users entitled for an upgrade, then patients fitted with Ponto between 7 and 12 months before visit 1 will be considered. If there are not enough users within 7-12 months, then patients fitted with Ponto between 13 and 18 months before visit 1 will be considered. 
Exclusion criteria
 
• Single-sided deafness (SSD)• Hearing aid or cochlear implant on the opposite ear.• Test persons with current eye diseases and/or history of eye surgery on both eyes.• If the patient takes medications that can impact the autonomic nervous system – and hence pupil dilation (e.g., drugs for Parkinson’s disease, peptic ulcers, incontinence, motion sickness).• If the investigator or physician assesses that the patient is not fit for trial participation.
Intervention(s) :	Patients are fitted with Ponto 4 sound processor.
Duration of study period:	Each patient will be enrolled in the study for approximately 4 months.
Criteria for safety:	No safety risk is expected.
Statistical methods:	Growth curve analysis, Mixed model ANOVA, Paired t-test / Wilcoxon signed rank test.
Investigation plan prepared by:	[name], Oticon Medical AB

1. Contents

1. ABBREVIATIONS	5
2. INTRODUCTION	5
3. IDENTIFICATION AND DESCRIPTION OF THE INVESTIGATIONAL DEVICE	6
4. PRELIMINARY INVESTIGATIONS AND JUSTIFICATION OF THE STUDY	6

1. ABBREVIATIONS

AE	Adverse Event
ANOVA	Analysis of Variance
BAHS	Bone Anchored Hearing System
CHL	Conductive Hearing Loss
CIP	Clinical Investigation Plan
CRF	Case Report Form
dB	Decibel
DFC	Dynamic Feedback Cancellation
ET camera	Eye Tracking camera
HI	Hearing Impaired
HINT	Hearing In Noise Test
HL	Hearing Loss
Hz	Hertz
MHL	Mixed Hearing Loss
OSN	OpenSound Navigator
PPD	Peak Pupil Dilation
SAE	Serious Adverse Event
SNR	Signal-to-Noise Ratio
SP	SuperPower
SPL	Sound Pressure Level
SSD	Single Sided Deafness
UCL	Uncomfortable Level

2. INTRODUCTION

The concept of listening effort has, for a long time, been difficult to quantify since it was typically assessed via questionnaires completed *after* a given task was performed. Today, several studies have shown that the pupil dilation can function as an objective indicator of listening effort *during* the execution of a task (Wendt et al., 2017; Zekveld et al., 2011; Ohlenforst et al., 2017). An eye-tracking camera can be used to measure the task-evoked pupil dilation in environments that differ in terms of listening demands. It has been shown that the pupil typically dilates as the task demands imposed by the listening situation increase (Beatty, 1982; Kahneman and Beatty, 1966). However, pupil size and task demands are not monotonically related. Pupil size follows an inverse U-shaped function of task demands, i.e., the pupil increases in size with increasing task demands up to a certain level of task demand. After this "maximum effort" point, the pupil size decreases in size suggesting that the listener "gives up" in the presence of a too demanding listening situation (Ohlenforst et al., 2018; Ohlenforst et al., 2017).

The focus of this study is to investigate listening effort during a speech-in-noise task, where task demands are systematically varied, in bone-anchored hearing systems (BAHS) users wearing the new bone-anchored sound processor from Oticon Medical AB (Ponto 4). The aim is to compare listening effort with different settings of Ponto 4's new feature, called OpenSound Navigator (OSN). The OSN feature is a Multi-Speaker Access Technology that can offer different levels of benefit to fit

different users' needs. In this study, we aim to evaluate the relationship between pupil size and task demands for different OSN settings in BAHS users. Additionally, the aim of this study is to investigate the relationship between pupil dilation and acclimatization with Ponto 4. Since it is unknown whether pupillometry is a sensitive measure to reflect acclimatization to a new bone-anchored device, this part of the study is completely novel and exploratory. Hence, the outcomes of this study may provide us with novel insights into listening effort in bone-anchored users, as well as acclimatization to a new sound processor and its impact on daily-life fatigue.

3. IDENTIFICATION AND DESCRIPTION OF THE INVESTIGATIONAL DEVICE

The investigational device used in this study is Ponto 4 – the bone-anchored sound processor developed by Oticon Medical AB (Askim, Sweden), which was released in June 2019 and is CE marked.

Ponto 4 is intended for improvement of hearing for patients with conductive or mixed hearing losses, whether unilaterally or bilaterally fitted, and for those with single sided deafness. Ponto 4 is intended to be used either with the Ponto implant system or with specific compatible abutments and implants. Ponto 4 can also be used on a softband. This study will only evaluate the sound processor on already implanted BAHS users. The use of the investigational device in this study will be within Ponto 4 intended purpose.

For the fitting of Ponto 4, Genie Medical BAHS 2019.1 will be used.

The devices used in the study will be traced with serial numbers. The serial numbers of the devices together with the test person identification number will be noted in the Case Report Form (CRF).

4. PRELIMINARY INVESTIGATIONS AND JUSTIFICATION OF THE STUDY

The concepts of fatigue, cognitive load, and listening effort have received increased attention in the past years (Pichora-Fuller et al., 2016), as it has become clear that the interplay between auditory and cognitive factors has a central role in everyday listening environments. The need to consider listening effort when evaluating a listening situation has become of great importance, especially because physiological measures of effort, such as pupillometry, have been shown to provide additional information beyond behavioral performance (Zekveld et al., 2010; Wendt et al., 2017; Ohlenforst et al., 2018). Hence, considering both perceptual and cognitive factors during listening tasks can provide a powerful framework to observe complementary aspects of effortful listening.

5. RISKS AND BENEFITS OF THE INVESTIGATIONAL DEVICE AND CLINICAL EVALUATION

The investigational device (Ponto 4) is fitted on users that are already Ponto users implanted with an abutment. Additionally, Ponto 4 will be fitted according to the manufacturer recommend fitting guidelines. Hence, the risk of participating in this study is low and comparable to corresponding rehabilitation outside this study. No risks are expected in regards to using Ponto 4 as investigational device. No disadvantages are expected for the subjects, other than the tiredness the patients can experience when listening to speech in noise and having to repeat speech. Any risk of using Ponto 4 in the patients's daily life is equal to that associated with the use of the patient's own Ponto device.

Additionally, the patient will be offered to keep the investigational device after the completion of the study if he/she wishes to do so.

There are no expected interactions of the treatment in this study with concomitant medical treatments or medication.

Three visits (of about 2 hours each) are included in this study, which is one extra visit as compared to normal standard care for patients that are switching BAHS sound processor.

It is therefore concluded that the risks associated with participation in this study are minimal and acceptable when weighed against the potential user benefits and the gain in terms of research results in a field important for long-term patient outcomes.

All adverse events will be registered and taken into consideration when compiling the final report.

6. OBJECTIVES AND HYPOTHESES

6.1 Primary Objective and hypothesis

- The primary objective of this study is to evaluate the decrease in pupil dilation when listening to speech-in-noise with OSN ON compared to OSN OFF at +4 dB SNR. The hypothesis is that OSN ON will lead to a significant reduction in pupil dilation (i.e., less listening effort) as compared to OSN OFF.

6.2 Secondary Objectives and hypotheses

The secondary objectives of this study are:

- To evaluate the difference in peak pupil dilation (PPD) when listening to speech-in-noise with OSN ON compared to OSN OFF across SNRs. The hypothesis is that there is a significant decrease in PPD with OSN ON vs. OSN OFF at SNRs lower than 5 dB but higher than the "give-up" point.
- To evaluate the difference in speech recognition scores with OSN ON compared to OSN OFF across SNRs. The hypothesis is that there is a significant increase in speech intelligibility with OSN ON vs. OSN OFF.
- To evaluate the change in overall pupil dilation, as calculated via Growth Curve Analysis, with OSN ON vs. OFF at different SNRs. The hypothesis is that the overall pupil dilation is significantly reduced with OSN ON compared to OSN OFF at SNRs lower than 5 dB but higher than the "give-up" point.
- To evaluate the change in overall pupil dilation after first fitting with Ponto 4 (visits 1 or 2), as calculated via Growth Curve Analysis, with OSN Auto vs. OFF at +4 dB SNR.
- To evaluate the change in overall pupil dilation after the field-trial period with Ponto 4 (visit 3), as calculated via Growth Curve Analysis, with OSN Auto vs. OFF at +4 dB SNR.

- To evaluate the change in overall pupil dilation, as calculated via Growth Curve Analysis, with OSN Auto vs. ON at +4 dB SNR. The hypothesis is that there is no significant difference in overall pupil dilation between OSN Auto compared to OSN ON.
- To evaluate self-reported performance (via the SSQ questionnaire) with Ponto 4 after 1 month field trial compared to own device.
- To evaluate self-reported performance (via the SSQ questionnaire) with Ponto 4 after 3 months field trial compared to own device.
- To evaluate self-reported performance (via the SSQ questionnaire) with Ponto 4 at 3-months follow up compared to 1-month follow up.
- Relationship between peak pupil dilation and speech recognition scores.
- Investigate the preference of Ponto 4 compared to own device.
- Investigate aided sound field thresholds with Ponto 4 and remaining air-to-bone gap (also known as BC gain or effective gain).

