7. DESIGN OF THE CLINICAL INVESTIGATION

This study is a single-center, single-blinded, prospective study on adults BAHS users, who are already experienced Ponto users (see inclusion criteria).

All participants will perform a speech-in-noise test at different SNRs and at three different Ponto 4 settings (OSN ON, OSN OFF, OSN Auto) while an eye-tracking camera records pupil dilation as an indicator of listening effort. The patients are blinded to the test condition. Patients that are bilaterally implanted, will be tested bilaterally with a Ponto 4 placed on each abutment. Patients that are unilaterally implanted will be tested with a Ponto 4 on the implanted side and the opposite ear will remain open and unaided. For the unilaterally fitted patients, no crucial contribution from the opposite side is expected to occur since they also have a hearing loss on the opposite ear (see inclusion criteria). All participants will perform all conditions and will act as their own control.

See Appendix A and B for a list of all conditions and time estimates.

Pupillometry at Visits 1 and 2

The tested conditions will be balanced across participants and across visits (see Figure 1 and Appendix B for the details). The three OSN settings (OSN ON, OSN OFF, OSN Auto) will be tested at the same visit for the same SNR to avoid differences in pupil dilation that could occur across visits (e.g., small differences in camera positioning, lighting, fatigue,...). The order of SNRs will be randomized within each OSN settings (see Figure 1). In a best attempt to maintain motivation constant within and across visits, easy and difficult conditions will be balanced across visits (i.e., SNRs of -8 dB, 0 dB, and +8 dB at one visit; SNRs of -4 dB and +4 dB at the other visit).

Two training lists (+4 dB SNR with OSN OFF, and -4 dB SNR with OSN ON) will be performed before starting the test at Visit 1. Since Visit 2 is scheduled within a week after Visit 1, only one training list will be performed before starting the test at Visit 2.

The setting OSN Auto will only be performed at +4 dB SNR. This SNR was specifically chosen to lead to a speech intelligibility performance, on average, above 50% – hence before the “give up” point, while still activating of the OSN feature. The OSN Auto condition will be tested either at Visit 1 or Visit 2, in between the other two settings (see Figure 1).

Field-trial period

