After the first two laboratory visits, the test person will undergo a field trial period of about 3 months, where Ponto 4 will be used in everyday life (with OSN set to Auto) instead of the patient's own Ponto.

Pupillometry at Visit 3

After the field trial period, a third visit will be performed, where the same speech-in-noise test will be carried out at two Ponto 4 settings (OSN Auto and OSN OFF), while an eye-tracking camera records pupil dilation. Two training lists (+4 dB SNR with OSN OFF, and +4 dB SNR with OSN Auto) will be performed before starting the test at Visit 3.

The test leader will change the test devices/programs when required by the test condition (OSN ON, OSN OFF, OSN Auto) and according to the SNR randomization for each patient.

Two questionnaires (SSQ and NfR) will also be completed in relation to the patient's own device (at Visit 1) and in relation to Ponto 4 after 3-months trial (at Visit 3) In addition, the SSQ will also be completed after 1-month trial with Ponto 4. A preference questionnaire will also be completed at Visit 3 to evaluate the preference of Ponto 4 vs. the patient's own device.

Finally, audiology (AC, masked BC) and sound-field thresholds (aided with Ponto 4) will be performed at Visit 3. These audiometric evaluations are performed at Visit 3 instead of Visit 1 to reduce the burden on the participants at Visit 1.

See the detailed study overview in Table 1.

[figure not shown]

Figure 1: Schematic showing the study conditions (SNRs and OSN settings) for pupillometry testing, balanced across patients and visits.

Table 1 Overview of the study visits.

	Visit 1	Visit 2 [1-10 days after visit 1]	Phone reminder [4-5 weeks after visit 2]	Visit 3 [12-15 weeks after visit 2]
Consent form	x			

BC in situ and fitting with Ponto 4	x			
Pupillometry	x	x		x
Field trial with Ponto 4		x (start)		x (end)
Audiometry (AC and masked BC)				x
Sound field audiometry				x (aided with Ponto 4)
SSQ questionnaire	x (reference device)		x (Ponto 4)	x (Ponto 4)
Need of recovery questionnaire (NfR)	x (reference device)			x (Ponto 4)
Preference questionnaire				x

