7.1.2 Secondary endpoints

- Difference in peak pupil dilation (PPD) between OSN ON and OSN OFF across SNRs.
- Difference in speech recognition scores between OSN ON and OSN OFF across SNRs.
- Difference in overall pupil dilation, as calculated via Growth Curve Analysis, between OSN ON and OSN OFF across SNRs.
- Difference in overall pupil dilation between OSN Auto and OSN OFF at +4 dB SNR (measured at visits 1 or 2), as calculated via Growth Curve Analysis.
- Difference in overall pupil dilation between OSN Auto and OSN OFF at +4 dB SNR (measured at visit 3), as calculated via Growth Curve Analysis.
- Difference in overall pupil dilation between OSN Auto and OSN ON at +4 dB SNR (measured at visits 1 or 2), as calculated via Growth Curve Analysis.
- Difference in SSQ scores between Ponto 4 after 1 month field trial and own device.
- Difference in SSQ scores between Ponto 4 after 3 months field trial and own device.
- Difference in SSQ scores between Ponto 4 after 1-month field trial and after 3-months field trial.
- Correlation between peak pupil dilation and speech recognition scores.

- Number of test subjects preferring Ponto 4.
- Sound scenarios for which test subjects significantly prefer Ponto 4 over own device.
- Difference in dB between aided thresholds and BC in-situ thresholds –i.e., remaining air-bone gap (also known as BC gain or effective gain).

7.1.3 **Tertiary endpoints**

- Difference in NfR scores with Ponto 4 after field trial and own device.
- Correlation between NfR scores and pupil dilation with Ponto 4 after field trial.
- Difference in overall pupil dilation (intercept term) between Visit 1-2 and Visit 3 for the contrast OSN Auto vs. OSN OFF.
- Difference in peak pupil dilation between Visit 1-2 and Visit 3 for the contrast OSN Auto vs. OSN OFF.
- Difference in the following parameters between Visit 1-2 and Visit 3 for the pupil curves obtained with OSN Auto and OSN OFF: rate of growth/decay (linear term), changes in the rate of growth/decay (quadratic term), and the steepness of the curve around inflection points (cubic term).
- Difference in speech recognition scores between Visit 1-2 and Visit 3 for OSN Auto and OSN OFF.
- Correlation between pupil dilation and the patient's PTA and characteristics (e.g., age, unilateral/bilateral implantation).
- Correlation between speech recognition scores and the patient's PTA and characteristics (e.g., age, unilateral/bilateral implantation).

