8.2.3 Fitting

Fitting will be performed by a trained audiologist at Queen Elizabeth Hospital. The fitting will follow the recommended fitting flow from the manufacturer. The Ponto 4 will be fitted with the NAL-NL1 rationale; a feedback measurement as well as a BC in-situ audiometry measurement will be conducted. Further and individualized fine tuning will not be performed, for comparison reasons, unless it is absolutely necessary. See Table 2 for an overview of the settings for each condition: OSN ON, OSN OFF, OSN Auto.

Table 2 Overview of Ponto 4-45 settings for OSN ON, OSN OFF, OSN Auto.

	OSN ON	OSN OFF	OSN Auto
Feedback measurement	X	X	X
DFC	As prescribed	As prescribed	As prescribed
BC in-situ audiometry	Copied from OSN Auto	Copied from OSN Auto	X

Fine tuning	No fine tuning	No fine tuning	Preferably no fine tuning
OpenSound Navigator: -Directionality settings -Open Sound transition	Full Directional Very High*	Omni N/A	Open Automatic Medium
Noise reduction complex	-9 dB	OFF	-7 dB (default)
Noise reduction simple	-3 dB	OFF	0 dB (default)

*When fitting the 'OSN ON – condition' the following steps will be followed:

1. Directionality settings will be set to Open Automatic;
2. Transition will be set to Very High;
3. Directionality settings will be set to Full Directional.

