8.3. Test setup and materials

8.3.1 Pupillometry

The setup for this study consists of five loudspeakers positioned at a distance of 1 m from the test participant (see Figure 1). An eye tracking camera will be placed in front of the test person approximately 60 cm from the eyes. The eye-tracking camera is the Pupil Labs. The camera will track the pupil size of the test person during the speech-in-noise task.

UK English sentences will be presented in a 4-talker babble background noise. The loudspeaker at the 0° azimuth position will playback the target speech signal. The remaining 4 loudspeakers will each playback one of the 4 overlapping babble talkers at +/-90° and +/-150° azimuth. Additionally, unmodulated speech-shaped noise (SSN) was added to the 4-talker babble to simulate a diffuse noise environment and to trigger the automatic control of the NR algorithms (as in Wendt et al., 2017). The SSN was added to the two competing talkers presented from the back at ±150° with an SNR of -1.8 dB (i.e., the SSN was presented at a lower level than the babble).

Each trial will start with a short silence, followed by a baseline with noise (see silence and baseline durations in Appendix A). The sentence will start after the baseline. After sentence offset, the participant will need to wait for 3 seconds before repeating the sentence (retaining window).

[figure not shown]

Figure 2 Loudspeaker and camera setup used for the speech-in-noise test. The participant will wear one or two Ponto 4 on abutment.

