12. STATISTICAL CONSIDERATIONS

The analysis of the primary endpoint will be performed via Growth Curve Analysis (Mirman, 2014) to compare the overall pupil dilation for OSN ON vs. OFF at +4 dB SNR. Growth Curve Analysis will also be used to evaluate differences in overall pupil dilation between OSN ON and OSN OFF at different SNRs, between OSN Auto and OSN OFF (before and after field trial), and between OSN Auto and OSN ON at +4 dB SNR.

Additionally, a mixed-model ANOVA (SNR and OSN setting as fixed factors; subject as random factor) will be used to analyze the peak pupil dilation (PPD) across SNRs. Only data of those patient that completed both Visit 1 and Visit 2 will be included in the final analysis. When applicable, post-hoc analysis will be performed via contrasts of least-square means to clarify at which SNRs the effect of OSN is significant (the p-values will be corrected for multiple comparisons using the Tukey method).

A mixed-model ANOVA (SNR and OSN setting as fixed factors; subject as random factor) will also be used to analyze the speech recognition scores across SNRs. When applicable, post-hoc analysis will be performed via contrasts of least-square means to clarify at which SNRs the effect of OSN is significant (the p-values will be corrected for multiple comparisons using the Tukey method).

A mixed model ANOVA will also be used to analyze the SSQ scores for Ponto 4 vs. own device, as well as for Ponto 4 at 1-month follow up vs. 3-months follow up.

A paired t-test or Wilcoxon sign-rank test will be used to compare the NfR scores with Ponto 4 compared to own device. Pearson's or Spearman's correlation between NfR scores and pupil dilation with Ponto 4 after field trial will be performed.

A Wilcoxon sign-rank test (two tailed) will be performed for each item of the preference questionnaire to test whether the distribution of the scores is significantly different than "No preference".

On all tests a significance level of 5% will be adopted. Correction for multiple comparisons will be performed where applicable.

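### OSN Auto versus ON: the hypothesis is a null result judged only by a 5% difference test, so non-significance would agree with it without showing that Auto matches ON

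*Combined protocol and SAP*

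**What the plan says.** Section 6.2 lists the comparison of OSN Auto with OSN ON at +4 dB SNR as a secondary objective and attaches a hypothesis to it: "The hypothesis is that there is no significant difference in overall pupil dilation between OSN Auto compared to OSN ON". The two Auto versus OFF objectives in the same list carry no hypothesis. Section 7.1.2 defines the matching endpoint as a difference in overall pupil dilation from Growth Curve Analysis, measured at visit 1 or 2.

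Section 12 names the contrast once, at the end of the sentence on Growth Curve Analysis of differences ("and between OSN Auto and OSN ON at +4 dB SNR"), and adds: "On all tests a significance level of 5% will be adopted". Neither document section gives an equivalence margin, a confidence-interval rule or a power figure for it. Section 12.1 sizes the trial on the primary ON versus OFF endpoint only.

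Two further places bear on the contrast:

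- **Settings.** Table 2 (section 8.2.3) programs the settings differently. ON is Full Directional with transition Very High and noise reduction of -9 dB (complex) and -3 dB (simple). Auto is "Open Automatic Medium" with -7 dB and 0 dB.
- **Baselines.** Section 8.3.1 refers to Appendix A for the silence and noise durations. Appendix A lists 2 s silence and 6 s noise for OSN Auto, and 3 s and 3 s for ON and OFF at visits 1-2. OFF at visit 3 is listed at 2 s and 6 s.

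**The concern.** A difference test can reject equality but cannot establish it. When the hypothesis itself is an absence of significance, a noisy estimate agrees with it as readily as a precise estimate near zero.

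This matters because the primary endpoint concerns ON, whereas in the field trial "Ponto 4 will be used in everyday life (with OSN set to Auto". Auto versus ON is the direct comparison between the setting tested for the primary endpoint and the setting worn for three months. Auto versus OFF shows whether Auto helps, not whether it helps as much as ON. A real difference is plausible, given the Table 2 values. With no rule for reading the result, a non-significant p-value could be taken to show that the two settings perform alike while the interval still includes a sizeable loss.

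The baseline entries add a second difficulty. Section 7 says the three settings "will be tested at the same visit for the same SNR to avoid differences in pupil dilation that could occur across visits". Different silence and noise periods before the sentence undercut that like-for-like aim. The effect could create an Auto-ON difference or hide one; the documents do not allow its size or direction to be derived.

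**Working it through.** **Inputs (section 12.1).** Pilot means at +4 dB SNR: ON 0.078, OFF 0.11. SDs: ON 0.09, OFF 0.08. Effect size 0.48, significance level 0.05, power 0.8, minimum n 29, planned n 30.

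**Reproducing the plan's figure.** With a paired t-test (noncentral t) and effect size 0.48, a one-sided 5% test needs n = 29 (power 0.810), which matches the plan. A two-sided test needs 37. The 0.48 therefore behaves as a paired standardised difference.

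**Implied SD of differences.**

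- Benefit: 0.11 - 0.078 = 0.032.
- SD of differences: 0.032 / 0.48 = 0.0667.
- Implied within-subject correlation: (0.09² + 0.08² - 0.0667²) / (2 × 0.09 × 0.08) = 0.70.

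The documents give no SD for Auto minus ON, so this value is carried over as an assumption. For other correlations r, SD = √(0.09² + 0.08² - 2r × 0.09 × 0.08).

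**Precision at n = 30.**

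- Standard error: 0.0667 / √30 = 0.0122.
- 95% CI half-width: 2.045 × 0.0122 = 0.025, and 0.025 / 0.032 is about 78% of the pilot benefit.
- Difference detectable with 80% power: 0.529 × 0.0667 = 0.035, about 1.1 times the benefit.

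**Probability of non-significance** (two-sided 5%, noncentrality = true difference / standard error). It is 0.95 under equality whatever the SD. Half loss means Auto is worse than ON by 0.016 (noncentrality 1.31). Full loss means worse by 0.032 (noncentrality 2.63). The last column is the probability, when Auto loses half the benefit, of finding Auto not significantly different from ON and also significantly better than OFF. It comes from simulation with the same SD of differences for every pair.

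| r | SD of differences | Half loss, non-significant | Full loss, non-significant | 95% CI half-width | Half loss: both findings |
|---|---|---|---|---|---|
| 0 | 0.120 | 0.89 | 0.71 | 0.045 | 0.10 |
| 0.5 | 0.085 | 0.83 | 0.49 | 0.032 | 0.16 |
| 0.70 | 0.067 | 0.75 | 0.28 | 0.025 | 0.22 |
| 0.8 | 0.055 | 0.66 | 0.13 | 0.020 | 0.29 |
| 0.9 | 0.039 | 0.42 | 0.01 | 0.015 | 0.31 |

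Under full loss the pair of findings occurs in about 2% of trials at r = 0.70. A multiplicity correction, which section 12 leaves unspecified, would make non-significance more likely.

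**Would a formal equivalence test work?** Power of two one-sided 5% tests at n = 30, true difference 0, SD 0.067: about 0.64 for a margin of 0.032 and 0.003 for 0.016. The approximate n for 80% power is 38 and 149.

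**Baselines in Appendix A, side by side.**

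| Comparison | Baselines (silence/noise) | Matched? |
|---|---|---|
| ON vs OFF, visits 1-2 (includes primary) | 3 s/3 s and 3 s/3 s | Yes |
| Auto vs ON, visits 1-2 | 2 s/6 s and 3 s/3 s | No |
| Auto vs OFF, visits 1-2 | 2 s/6 s and 3 s/3 s | No |
| Auto vs OFF, visit 3 | 2 s/6 s and 2 s/6 s | Yes |
| Change in Auto-OFF contrast, visits 1-2 to visit 3 (tertiary) | OFF changes from 3 s/3 s to 2 s/6 s | No |

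**The case against.** The plan never mentions equivalence or non-inferiority, does not say that non-significance will be reported as equality, and rests no decision on this contrast, which is one of 13 secondary endpoints. The benefit of the worn setting is tested directly by Auto versus OFF, and the questionnaires concern Ponto 4 as worn. All of that is true. It limits the weight of the point but does not supply the missing reading rule: the stated hypothesis is still met by p > 0.05 alone.

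The figures are illustrative, and that stands too. The pilot values are peak dilations, the endpoint is a growth-curve intercept from a mixed model, and the correlation of 0.70 is back-calculated. The ranges are wide, and on the central assumption a full loss is separated from equality reasonably well (28% against 95%). In the half-loss case a finding that Auto beats OFF would be correct; only an added reading of equality with ON would mislead. If Auto and ON are more alike than the other pairs (SD of their difference 0.047 or 0.039), the 22% falls to about 18% or 14%.

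The Appendix A row may be a typing error. The table also gives visit 3 training as -4 dB SNR with OSN ON, where section 7 describes Auto and OFF at +4 dB. That is a reason to reconcile the entry, not to ignore it, because section 8.3.1 makes the table the operative specification.

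On timing, section 7.4 schedules an interim analysis for November 2019 and this revision was released in February 2020, so a change now may follow an interim look.

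**Conclusion.** The concern holds. The Auto versus ON hypothesis can be met by a non-significant result that does not show the two settings to be alike. On the central assumption (n = 30, two-sided paired test, SD of differences 0.067), half of the pilot benefit could be lost and the test would still be non-significant about three times in four; the range is 89% to 42% for correlations of 0 to 0.9. These sizes depend on pilot peak-dilation variability carrying over to the Auto-ON intercept. The logical point does not depend on them.

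As Appendix A is written, Auto versus ON and Auto versus OFF at visits 1-2, and the tertiary change between visits, also mix setting with baseline by an unknown amount.

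The primary endpoint is untouched on both counts. This should be corrected, but it does not threaten the main result.

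**What to change.** Replace the hypothesis sentence in section 6.2, and add the same rule to section 12:

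> The Auto minus ON difference in overall pupil dilation will be estimated with its 95% CI; a non-significant p-value will not be interpreted as equivalence.

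An equivalence claim is optional. It would need a margin justified in advance on the intercept scale, and at n = 30 it would probably be underpowered.

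Separately, reconcile the Appendix A baseline entries so that settings compared with each other share the same durations. If the listed difference is real and sessions have already been run that way, report it as a limitation of Auto versus ON and Auto versus OFF at visits 1-2 and of the tertiary comparison between visits.

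The cost is one sentence in each of two sections and a check of one table, with no new patients or data. The sponsor gives up a statement of no difference unless the interval supports it. The change should be documented as an amendment, stating whether it came before or after any interim look at the data.
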